9.3 LIST OF SAFETY FSR TABLES

- Enrollment Report
- Demographics and Study Product Administration Frequencies
- Overall Protocol Status
- Discontinuation Status Listing
- Study Product Administration Errors Listing
- Maximum Local Reactogenicity Summary
- Maximum Systemic Reactogenicity Summary
- Severe or Life-Threatening Local Reactogenicities Listing
- Severe or Life-Threatening Systemic Reactogenicities Listing
- Moderate, Severe, or Life-Threatening Erythema/Induration Listing
- AEs by Body System and Severity
- AEs by Preferred Term and Severity – Includes Severe, Life-Threatening, or Fatal Events Only
- AEs by Preferred Term and Severity – Includes All Severities
- AEs by Preferred Term and Severity – Includes Related Events Only
- AEs by Preferred Term and Severity – Includes Events Related to the EP Device Only

- AEs by Preferred Term and Relationship to Study Product – Includes Events of Any Relationship
- Severe, Life-Threatening, or Fatal Adverse Events Listing
- Adverse Events of Special Interest Listing
- Related Adverse Events Listing
- Device Related Adverse Events Listing
- EAEs Reported to the RSC Listing
- Pregnancy Listing
- HIV Infection Listing
- Listing of Device-Only Participants
- Listing of Device-Only Participant AEs
- Social Impact Summary
- End of Study Diagnostic Testing Results for Vaccinees
- EP Acceptability Questionnaire Results
- Local Lab Values Meeting Grade 1 AE Criteria or Above
- Local Lab Value Summary Statistics Tables

9.4 LIST OF SAFETY FSR FIGURES

- Maximum Local Reactogenicities
- Maximum Systemic Reactogenicities
- Boxplots for platelets, WBC, lymphocytes, neutrophils, hemoglobin, alkaline phosphate, AST, ALT, and creatinine at baseline and each post-vaccination follow-up visit
- Boxplots with visual analog scale (VAS) pain assessment scores at each vaccination visit

10. ASSAY-SPECIFIC TABLES AND FIGURES FOR PROTOCOL TEAM REPORTS

10.1 Binding Antibody Multiplex Assay (BAMA)

Serum HIV-1-specific IgG antibody responses are measured at the 1:50 dilution against the p24^{agg} antigen on all available samples at visit 2 (month 0/baseline) and visit 11 (Month 6.5/2 weeks post 4th vaccination) (Tomaras and Yates et al., J Virology 2008). The assay readout is from a Bio-Plex instrument (Bio-Rad). The Bioplex software provides 2 readouts: a background-subtracted mean fluorescent intensity (MFI), where background refers to a plate level control (i.e., a blank well run on each plate), and a concentration based on a standard curve. Net MFI (MFI*) is MFI minus Neg, where 'Neg' refers to a sample-specific background measure. Samples from post-enrollment visits are declared to have positive responses if they meet three conditions: (1) the MFI* values are greater than the antigen-specific cutoff (based on the 95th percentile of the baseline visit serum samples and at least 100 MFI), (2) the MFI* values are greater than 3 times the baseline (day 0) MFI* values, and (3) the MFI values are greater than 3 times the baseline MFI values. Net MFI is used to summarize the magnitude at a given time-point. If sufficient immunogenicity is observed, samples may be

titrated to calculate antibody titers. Titrations are quantified by EC50/AUC. If titrations are performed, the geometric mean titer will be compared between the treatment groups. The overall difference in geometric mean titer between groups at each time point will also be compared.

Several criteria are used to determine if data from an assay are acceptable and can be statistically analyzed. The blood draw date must be within the allowable visit window as determined by the protocol. Second, if the blank bead negative control exceeds 5,000 MFI, the sample will be repeated. If the repeat value exceeds 5,000 MFI, the sample will be excluded from analysis due to high background.

The following comparisons of the immune response rates and magnitude (MFI* values (overall and among positive responders only)) will be done:

- Fisher's exact test and Barnard's test are used to compare response rates between pairs of groups, and the Wilcoxon rank sum test is used to compare response magnitudes (net MFI) among positive responders between pairs of groups. Group comparisons include T1 vs. control (pooled), T2 vs. control (pooled), and T1 vs. T2. P-values are two-sided and unadjusted for multiple comparisons.

Contingent upon these results, assays may be performed on additional timepoints, isotypes, and/or antigens.

List of Tables

Tables are stratified by lab, isotype, antigen, visit number, visit month, and treatment group.

- Response rate table by isotype, antigen, visit, and treatment group. Positivity criteria will be stated in footnote.
- Summary statistics (minimum, 25th percentile, median, 75th percentile, maximum, mean, standard deviation) among all participants, by treatment group.
- Summary statistics (minimum, 25th percentile, median, 75th percentile, maximum, mean, standard deviation) among positive responders, by treatment group.
- Listing of magnitudes (MFI* values) among positive responders.
- Response rate comparisons.
- Response magnitude comparisons among positive responders, if there are at least 5 responders within each group at a given visit.

List of Figures

Figures are stratified by lab, isotype, antigen, visit number, visit month, and treatment group.

- Boxplots of MFI* values by isotype, antigen, visit, and treatment group. Individual-level data for post vaccination visits will be connected by lines, with treatment group side by side, one isotype and antigen per graph.
- Reverse CDFs of MFI* by isotype, antigen, visit, and treatment group.

- If titrations are measured, boxplots of binding titration (EC50/AUC) by isotype, antigen, visit and group/treatment arm. Individual-level data for post vaccination visits will be connected by lines, with treatment group side by side, one isotype and antigen per graph.

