IAVI has presented results of its B004 study, which also tested multiple injections of HIV-MAG and GENEVAX[®] *IL-12-*4532 DNA IM/EP (Ichor TDS-IM EP Device) in healthy volunteers [7]. The study tested the groups shown in Table 4-3. The vaccine regimens tested were adequately safe with no SAEs or AEs that were probably or definitely related to vaccine. The vaccine regimens in the 3 study groups shown were similarly rated with respect to tolerability.

With respect to cellular responses assessed by IFN- γ ELISpot, at baseline there were no responders. After the 3 pDNA priming injections, response rates among vaccinees were 82% (9/11) in Group 1, 64% (7/11) in Group 2, and 42% (5/12) in Group 3. After the Ad35-GRIN/ENV boost, response rates among vaccinees were 73% (8/11) in Group 1, 82% (9/11) in Group 2, and 89% (8/9) in Group 3. Samples from 8 participants in each group were also assessed with 7-color ICS to assess expression of IL-2, TNF- α , and IFN- γ in response to peptides matched to the HIV-MAG vaccine. Groups 1-3 had similar CD4+ and CD8+ T-cell response rates and magnitudes, and the polyfunctionality profiles were similar. An ELISA assay for HIV-specific antibodies to Env A and Env B (matched to the HIV-MAG vaccine) and p24^{Gag} did not detect any HIV-specific antibodies following the DNA primes in any group. In summary, the vaccine regimens tested were immunogenic, but there was no clear indication of enhancement of immunogenicity of HIV-MAG by IL-12 DNA in this small trial. One shortcoming of this data is that the participants were not all evaluated for CD8+ responses with ICS. It is not clear how the specific participant samples were selected for ICS assay, or how responses would have differed if measured by the HVTN laboratory assays.

Study arm	Ν	Month (Week)	Month (Week)	Month (Week)	Month (Week)
	1	0 (0)	1 (4)	2 (8)	6 (24)
	12	HIV-MAG	HIV-MAG	HIV-MAG	Ad35-GRIN/ENV
Group 1	3	Placebo	Placebo	Placebo	Placebo
Group 2	12	HIV-MAG+ IL-12 pDNA 0.1 mg	HIV-MAG+ IL-12 pDNA 0.1 mg	HIV-MAG+ IL-12 pDNA 0.1 mg	Ad35-GRIN/ENV
	3	Placebo	Placebo	Placebo	Placebo
Group 3	12	HIV-MAG+ IL-12 pDNA 1 mg	HIV-MAG+ IL-12 pDNA 1 mg	HIV-MAG+ IL-12 pDNA 1 mg	Ad35-GRIN/ENV
	3	Placebo	Placebo	Placebo	Placebo

Table 4-3 B004 schema

Note: HIV-MAG 3 mg delivered IM by EP. GENEVAX[®] IL-12 DNA plasmid co-administered with HIV-MAG delivered IM by EP. Ad35-GRIN/ENV 2×10¹⁰ vp delivered IM by standard needle injection.

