6.1.2 Sample size calculations for immunogenicity

For comparing the CD4+ and CD8+ T-cell endpoints between the 2 vaccine regimens, the primary analysis uses head-to-head superiority comparisons. The comparison will be performed separately for each of the primary breadth and secondary magnitude T-cell subset endpoints. No multiplicity adjustments are made for the multiple comparisons given the utility to favor higher power at the expense of a higher accepted false positive rate.

Figure 6-1 below summarizes power available for superiority testing. For these calculations, we assume 17% missing data (n=21 evaluable endpoints from each arm). Sample size calculations for breadth of response are based on data from the HVTN 083 trial and assume a beta-binomial distribution. Sample size calculations for ICS magnitude assume normally distributed magnitudes after natural log transformation with standard deviation = 1. The assumptions for the sample size calculations for ICS magnitude are based on the data from the HVTN 080 trial. Superiority test power is based on the Mann-Whitney U test with 2-sided p-value <0.05 as statistically significant.

If mean CE breadth in the vaccine recipients in Group 1 is 0.2 (0.5) then the study has 80% power to detect superiority in Group 2 if the true CE breadth the 2^{nd} group is at least 1.0 (1.5). A 2.5 fold-change in the vaccine recipients from Group 2 versus Group 1 is required to have 80% power to detect superiority in the T-cell response magnitude.

[figure not shown]

Figure 6-1 Power to detect superiority in CE Breadth and ICS Magnitude. Power calculations for the breadth of response were run under two different scenarios. In the first panel power the mean CE Breadth is assumed to be 0.2 for the vaccine recipients in Group 1 while the second panel assumes a mean CE Breadth of 0.5. In the third panel power calculations are shown for the magnitude of response. The x-axis in the first two panels is the CE Breadth for the vaccine recipients in Group 2 and for the third panel it the x-axis is the fold change in ICS response magnitude for vaccine recipients from Group 2 versus Group 1. Power curves are shown for N=20, 25, and 30 vaccine recipients per Group and account for 17% missing immunogenicity data.

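### SAP 10.1 measures day-0 p24 IgG but adjusts no visit-11 magnitude comparison for it, so the overall T1 v T2 comparison may lose some precision

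*SAP*

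**What the plan says.** SAP 10.1 measures p24 IgG "on all available samples at visit 2 (month 0/baseline) and visit 11" (2 weeks after the fourth vaccination). Net MFI is MFI less a sample-specific background, and "Net MFI is used to summarize the magnitude at a given time-point".

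Day 0 is used to decide who is a responder. Visit-11 MFI and net MFI must each exceed three times the participant's own baseline, and net MFI must exceed a cutoff built on the 95th percentile of baseline sera (at least 100 MFI).

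For magnitude, 10.1 announces comparisons both overall and among positive responders, then names one test: "the Wilcoxon rank sum test is used to compare response magnitudes (net MFI) among positive responders between pairs of groups". The table list adds that this comparison needs at least 5 responders in each group. Nothing in 10.1 says how the overall comparison is to be tested, so the general rule in SAP 8.4.1 applies: Wilcoxon rank sum or two-sample t-test, with no covariate. SAP 8.4.1 brings in baseline covariates only through the models reserved for more than 20% of participants with missing data.

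**The concern.** Participants may carry some person-specific reactivity to the antigen before vaccination. Subtracting a sample background does not remove it. If it persists to day 182, it adds spread to visit-11 net MFI that has nothing to do with the regimen, and a chance imbalance at day 0 carries over in part into the T1 v T2 contrast. The plan already collects the value that would remove this spread, yet no magnitude comparison uses it as a covariate.

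At stake is precision on the magnitude half of secondary endpoint 3. Validity is not in question: randomisation keeps the unadjusted test unbiased and at its nominal size.

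**Working it through.** **Inputs from the documents.** Protocol 6.1.2: "we assume 17% missing data (n=21 evaluable endpoints from each arm"; "Superiority test power is based on the Mann-Whitney U test with 2-sided p-value <0.05 as statistically significant"; ICS magnitudes are taken as "normally distributed magnitudes after natural log transformation with standard deviation = 1". No SD, effect size or power is stated for the antibody assay.

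**Assumptions.** rho, the within-arm correlation of day-0 and day-182 net MFI, is varied from 0 to 0.5. Data are bivariate normal. The shift is 0.7 SD, with 2.5-fold at ln-scale SD 1 as a second case.

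**1. The plan's own figure.** The protocol states: "A 2.5 fold-change in the vaccine recipients from Group 2 versus Group 1 is required to have 80% power to detect superiority". Here 25 x 0.83 = 20.75, rounded to 21, and ln 2.5 = 0.916. Simulating the Mann-Whitney test with 21 per arm, shift 0.916 and SD 1 gives 80.8%, so the 80% reproduces. It is an ICS figure and serves only to calibrate the method.

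**2. Rank ANCOVA in all evaluable participants.** Quade's method ranks visit-11 and visit-2 values over both arms, regresses one set of ranks on the other, and compares the residuals between arms. Simulated power, 21 per arm, 0.7 SD shift, two-sided 0.05:

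| rho | Mann-Whitney | Quade | Change (points) |
|---|---|---|---|
| 0 | about 57% | 56-57% | about -0.5 |
| 0.2 | about 57% | about 58% | about +1 |
| 0.3 | about 57% | 60-61% | +3 to +4 |
| 0.5 | about 58% | 67-68% | about +10 |

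At a 2.5-fold shift the changes are about -0.8 point at rho 0 (79.1% v 79.9%), -0.2 at rho 0.1 (80.2% v 80.4%), +2 at rho 0.3 and +8 at rho 0.5. Size stays at about 5% throughout.

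**3. Why not among responders.** For linear ANCOVA with N analysed, variance relative to the unadjusted comparison is (1 - rho^2) x (N-3)/(N-4). Values below 1 are a gain.

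| rho | N = 42 | N = 20 | N = 10 |
|---|---|---|---|
| 0 | 1.03 | 1.06 | 1.17 |
| 0.2 | 0.985 | 1.02 | 1.12 |
| 0.3 | 0.93 | 0.97 | 1.06 |
| 0.5 | 0.77 | 0.80 | 0.875 |

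Break-even is rho = sqrt(1/(N-3)): 0.16 at N = 42, 0.24 at N = 20, 0.38 at N = 10. With 5 responders per arm, the SAP's minimum, adjustment raises the variance unless rho exceeds 0.38. These factors do not depend on the SD.

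**4. Chance imbalance.** The standard error of the day-0 mean difference is sqrt(2/21) = 0.309 SD, so an imbalance above 0.5 SD has probability 0.105. It moves the unadjusted contrast by rho x 0.5 SD or more: 0.15 SD at rho 0.3, 0.25 SD at rho 0.5.

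**The case against.** **Rho may be low.** Protocol 7.1 requires a negative HIV enzyme immunoassay and Protocol 7.2 excludes prior HIV vaccine recipients, so day-0 signal may be mostly assay background. This stands as the main limit on the gain. It does not settle rho: a negative screening assay does not establish that signal at 1:50 dilution is zero, and the SAP's own three-times-baseline rules guard against person-specific reactivity.

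**High rho and a large regimen effect pull against each other.** A strong vaccine response adds variance unrelated to day 0. Simulated mixtures of stable background plus a vaccine signal in part of each arm gave rank correlations from 0.03 to 0.38 and gains from -0.4 to +5 points under one set of assumptions. Under others they gave correlations of 0.49 and 0.61, with power rising from 26% to 32% and from 29% to 43%. All these parameters are assumed, so the range is the honest answer.

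**A reader might infer that the plan ignores day 0.** It does not. Day 0 defines the responders, and so shapes the response-rate comparison and decides who enters the named magnitude test.

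**A reader might take the gains above as the loss from the named test.** They are not. That test is restricted to responders, whereas the table describes all 21 per arm. The number of responders matters more there: with the ICS SD borrowed, Wilcoxon power at 2.5-fold is about 17% with 5 per arm against 81% with 21.

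**A reader might use the cited ELISA result** (Protocol 4.10.3: "did not detect any HIV-specific antibodies following the DNA primes in any group") as evidence of a high rho. It concerns a different DNA vaccine and says nothing about pre-existing p24 reactivity.

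**Other routes exist.** SAP 8.4.1 allows mixed models or GEE over timepoints, but only as an option, and by-visit tables would show an imbalance without correcting for it.

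**Conclusion.** The gap is real and modest. Day-0 IgG is measured, no visit-11 magnitude comparison adjusts for it, and the overall comparison has no test of its own in SAP 10.1. The plan may therefore lose precision on secondary endpoint 3. For 21 per arm and a 0.7 SD shift, adjustment is worth between about -0.5 point (rho 0) and about +10 points (rho 0.5).

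The documents do not support saying that precision is lost, because they give neither rho nor an SD for this assay. Nor is recovery strictly free: adjustment costs a fraction of a point at rho near 0, and more in a small responder subset. The case for changing rests on the asymmetry in the full set: a cost under 1 point against a possible gain of several. The figures assume bivariate normal data and 21 evaluable per arm with valid values at both visits. They cover T1 v T2 only; the control contrasts, with 6 placebo recipients in all, were not simulated for power.

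**What to change.** In SAP 10.1, give the overall T1 v T2 magnitude comparison its own test: Quade's rank ANCOVA of visit-11 net MFI with visit-2 net MFI as covariate, in all evaluable participants. Keep the unadjusted Wilcoxon on the same participants as a sensitivity analysis. Leave the responder-only Wilcoxon unadjusted.

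The cost is SAP wording and a few lines of code, with no new samples or assays. Participants without a valid day-0 value drop out of the adjusted analysis but stay in the sensitivity analysis; the positivity rules already need that value. SAP section 1 provides for an update before additional immunogenicity analyses. The change should be fixed before the visit-11 antibody data are analysed by arm, so that the choice is not made after seeing them.

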10.2 Intracellular Cytokine Staining Assay (ICS)

HIV-1-specific CD4+ and CD8+ T-cell responses are measured by intracellular cytokine staining as previously described (De Rosa, 2012 & Horton, 2007). A validated 28-color panel (experiment Assay ID 114; analysis plan 048) is used to evaluate Gag CE total and Gag p55 peptides at visit 6 (month 1.5/2 weeks post 2nd vaccination) and visit 11 (Month 6.5/2 weeks post 4th vaccination). CD4+ and CD8+ T cells expressing IL-2 and/or IFN- γ are included in the primary analysis. Marginal expression of CD40L for CD4+ T cells are included as a secondary analysis.

Several criteria are used to determine if data from an assay were acceptable and could be statistically analyzed. The blood draw date must have been within the allowable visit window as determined by the protocol. Post-infection samples from HIV-infected participants are excluded. After sample thawing and overnight incubation, the viability of the PBMC must have been 66% or greater for testing to have proceeded. If it was not, a new specimen for that participant at that time point was thawed for testing. If the PBMC viability of the second thawed aliquot was below this threshold, the ICS assay was not performed and no data were reported to the statistical center for the participant-time point. For the negative control acceptance criteria, if the average cytokine response for the negative control wells was above 0.1% for either the CD4+ or CD8+ T cells, the sample was retested. If the retested results were above 0.1%, the data were excluded from analysis; otherwise, the retest data were used.

The total numbers of CD4+ and CD8+ T cells must also have exceeded certain thresholds. If the number of CD4+ T cells was < 10,000 or the number of CD8+ T cells was < 5,000 for any of the HIV-1 peptide pools or for one of the negative control replicates for a particular sample, data for that stimulation were filtered. If both negative control replicates failed for number of T cells, the sample was retested. If one negative control replicate failed for number of T cells, the negative control replicate with sufficient cells was used.

To assess positivity for a peptide pool within a T-cell subset, a two-by-two contingency table was constructed comparing the HIV-1 peptide stimulated and negative control data. The four entries in each table were the number of cells positive for IL-2 and/or IFN- γ and the number of cells negative for IL-2 and IFN- γ for both the stimulated and the negative control data. If both negative control replicates were included, then the average number of total cells and the average number of positive cells were used. A one-sided Fisher's exact test was applied to the table, testing whether the number of cytokine-producing cells for the

stimulated data was equal to that for the negative control data. Since multiple individual tests (for each peptide pool) were conducted simultaneously, a multiplicity adjustment was made to the individual peptide pool p-values using the Bonferroni-Holm adjustment method. If the adjusted p-value for a peptide pool was ≤ 0.00001 , the response to the peptide pool for the T-cell subset was considered positive. Because the sample sizes (i.e., total cell counts for the T-cell subset) were large, e.g., as high as 100,000 cells, the Fisher's exact test has high power to reject the null hypothesis for very small differences. Therefore, the adjusted p-value significance threshold was chosen stringently (≤ 0.00001). If at least one peptide pool for a specific HIV-1 protein was positive, then the overall response to the protein was considered positive. If any peptide pool was positive for a T-cell subset, then the overall response for that T-cell subset was considered positive.

The following comparisons of the immune response rates and magnitudes (among positive responders only) will be done:

- Fisher's exact test and Barnard's test are used to compare response rates between pairs of groups, and the Wilcoxon rank sum test is used to compare response magnitudes among positive responders between pairs of groups. Group comparisons include T1 vs. control (pooled), T2 vs. control (pooled), and T1 vs. T2. P-values are two-sided and unadjusted for multiple comparisons.

Contingent upon these results, additional assays and/or analyses may be performed.

The following comparisons of FS and PFS will be done:

- Wilcoxon rank sum tests are used to compare FS and PFS between pairs of groups at each visit. Group comparisons include T1 vs. control (pooled), T2 vs. control (pooled), and T1 vs. T2. P-values are two-sided and adjusted for multiple antigens and visits via the false-discovery rate (FDR) method. Comparison results are considered statistically significant if p-value < 0.05 and the FDR-adjusted q-value < 0.2 .

List of Tables

Tables are stratified by T cell subset, cytokine, antigen, visit number (visit month), and treatment group.

- Response rate table by T cell subset, cytokine, antigen, visit number (visit month), and treatment group.
- Summary statistics (minimum, 25th percentile, median, 75th percentile, maximum, mean, standard deviation) among all participants, by T cell subset, cytokine, antigen, visit number (visit month), and treatment group.
- Summary statistics (minimum, 25th percentile, median, 75th percentile, maximum, mean, standard deviation) among positive responders, by T cell subset, cytokine, antigen, visit number (visit month), and treatment group.

- Listing of magnitudes among positive responders.
- Response rate comparisons.
- Response magnitude comparisons among positive responders, if there are at least 5 responders within each group at a given visit.
- Summary statistics (minimum, 25th percentile, median, 75th percentile, maximum, mean, standard deviation) of FS and PFS by T-cell subset, HIV protein, visit, and treatment group.
- FS and PFS comparison between treatment groups by T-cell subset, HIV protein, and visit.

List of Figures

Figures are stratified by T cell subset, cytokine, antigen, visit number (visit month), and treatment group.

- Boxplots of background-subtracted percent of cells expressing IL-2 and/or IFN- γ by T cell subset, antigen, visit number (visit month), and treatment group.
- Spaghetti plots of background-subtracted percent of cells expressing IL-2 and/or IFN- γ over time, by T cell subset, antigen and treatment group.
- Reverse CDFs of background-subtracted percent of cells expressing IL-2 and/or IFN- γ and/or CD40L by T cell subset, antigen and treatment group.
- Individual heatmaps showing posterior probabilities of antigen-specific responses from COMPASS by T-cell subset, HIV protein, and visit.
- Summary heatmaps showing posterior probabilities of antigen-specific responses from COMPASS by T-cell subset, HIV protein, and visit.
- Boxplots of FS/PFS by treatment group, T-cell subset, HIV protein, and visit.

